2.1 Main objectives

The main purpose of this study was to evaluate the nutritional status of patients undergoing maintenance peritoneal dialysis with amino acid peritoneal dialysate the effect of improvement.

2.2 Secondary objectives

The secondary aim of this study was to explore the metabolic status of patients undergoing maintenance peritoneal dialysis with amino acid peritoneal dialysate effects on residual renal function, dialysis adequacy and safety.

2.3 Exploratory purposes

According to $Kt/V \geq 1.7$, patients were divided into dialysis adequate and non-dialysis adequate groups, and the effects of amino acid peritoneal dialysate on the nutritional status of patients with dialysis adequacy were explored; according to Nt-pro BNP levels, patients

were divided into non-heart failure groups and heart failure groups for further exploration safety of amino acid peritoneal dialysis fluid.

3. Test design

The experimental design of this study is as follows:

3.1 Research design

This study adopts a multicenter, open, prospective, and self-controlled design, where each participant serves as their own control before and after receiving amino acid peritoneal dialysis fluid treatment, to compare changes in their nutritional status. This study does not set up a placebo or control group, as amino acid peritoneal dialysis fluid is already on the market, with its efficacy and safety proven, and there are no equivalent alternatives. The primary objective of this study is to observe the nutritional improvement effects and safety assessment of amino acid peritoneal dialysis fluid for malnourished peritoneal dialysis patients. Specific techniques

The route is shown in Figure 1:

[figure not shown]

Figure 1. Technical route

3.2 Study endpoints and evaluation criteria

3.2.1 Main end indicators

The primary endpoint of this study was the improvement of nutritional status of subjects after 3 months and 6 months of treatment, it includes the following two indicators:

- 1) Serum albumin (g/L): the change value of serum albumin compared with baseline at 3 months and 6 months after treatment (Δ serum albumin);
- 2) Prealbumin (mg/L): the change value of prealbumin at 3 months and 6 months after treatment. The change value of prealbumin compared with the baseline after month (Δ prealbumin); The treatment was considered effective if the difference in change from baseline for any of the above indicators was statistically significant.

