3.3.1 Selection criteria

1. Select patients with uremia with malnutrition during the screening period and maintain peritoneal dialysis for at least 3 months. Malnutrition

The standard shall at least meet two of the following items:

(1) Serum albumin level <3.5g/dL (35g/L),

(2) Prealbumin <300mg/L,

(3) Subjective comprehensive nutritional assessment (SGA)> 7 points;

2. Blood urea nitrogen \leq 38mmol/L;

3. The patient is between 18 and 75 years of age;

4. The patient signs an informed consent form.

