The daily use of 1 bag of amino acid peritoneal dialysis fluid is during the nighttime sleep period, while the daily use of 2-4 bags of glucose peritoneal dialysis fluid is during the daytime. The total daily infusion volume, each infusion volume, dwell time, and each excretion volume for each subject are adjusted by the researcher based on individual patient conditions and standardized prescriptions. During treatment, subjects should follow the researcher's guidance for daily life and dietary management, and regularly visit the research center for follow-up and examinations. In the third and sixth months of treatment, subjects should repeat the screening period

All evaluation items and any adverse events or serious adverse events are recorded.

The research process is shown in Table 1:

Table 1: Research process table

Evaluate projects	Screening period/baseline	stage of therapy					
		1 month	2 months	3 months	4 months	5 months	6 months
informed consent	√	×	×	×	×	×	×
Inclusion and exclusion criteria	√	×	×	×	×	×	×
Collect demographic data	√	×	×	×	×	×	×
Symptoms (loss of appetite, nausea, vomiting, abdominal distension, Infusion pain, edema, etc.)	√	√	√	√	√	√	√

Previous illness/treatment	✓	✗	✗	✗	✗	✗	✗
Combination therapy with concomitant medication	✓	✓	✓	✓	✓	✓	✓
allergic history	✓	✗	✗	✗	✗	✗	✗
SGA	✓	✓	✓	✓	✓	✓	✓
check-up	✓	✓	✓	✓	✓	✓	✓
vital sign	✓	✓	✓	✓	✓	✓	✓
Ultrafiltration volume	✓	✓	✓	✓	✓	✓	✓
UPD	✓	✓	✓	✓	✓	✓	✓
BMI	✓	✓	✓	✓	✓	✓	✓
CI	✓	✗	✗	✓	✗	✗	✓
skin-fold thickness	✓	✗	✗	✓	✗	✗	✓
Waist circumference and grip strength, upper arm muscle circumference	✓	✗	✗	✓	✗	✗	✓
Hepatitis B related antigen antibody, hepatitis C antibody, HIV antibody	✓	✗	✗	✗	✗	✗	✗
Biochemistry and liver and kidney function (including serum albumin, Prealbumin), glycosylated hemoglobin	✓	✗	✗	✓	✗	✗	✓
White, fasting blood sugar							
Nt-Pro BNP	✓	✗	✗	✓	✗	✗	✓
nPCR	✓	✗	✗	✓	✗	✗	✓

nPNA	✓	✗	✗	✓	✗	✗	✓
Kt/V and Ccr	✓	✗	✗	✓	✗	✗	✓
PET	✓	✗	✗	✓	✗	✗	✓
adverse event	✓	✓	✓	✓	✓	✓	✓

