7.1 Sample size calculation

This study is a post-marketing study, and a total of 140 subjects are planned to be included. The efficacy evaluation standard is 6 months of treatment

If the difference between the post-relative baseline change of Δ serum albumin or Δ prealbumin is statistically significant, it is considered

The treatment was effective. Based on the above hypothesis, a single sample self-preceding and following control design and a unilateral difference test were used

Quantity estimation formula:

$$n = \frac{(z_{\alpha} + z_{\beta}) \sigma^2}{\delta^2}$$

δ is the difference; σ is the standard deviation, which will be replaced by the sample size standard deviation.

The Hochberg method was considered to adjust for multiple endpoints, with the smallest test level $\alpha/2= 0.0125$ (one-sided) and power $(1- \beta) = 0.9$, based on the sample size estimates for different primary efficacy endpoints count.

1) Based on Δ serum albumin: According to the literature, it is assumed that the baseline serum albumin before treatment is 27 g/L, and the serum albumin after 6 months of amino acid peritoneal dialysis treatment is 28.5g/L, δ is 1.5g/L, and the standard deviation is 4.5 g/L,

The required sample size for the calculation was 112.

2) Based on Δ prealbumin: According to the literature, it is assumed that the baseline prealbumin before treatment is 240 mg/L, the prealbumin 6 months after amino acid peritoneal dialysis treatment is 300mg/L, δ is 60mg/L, and the standard deviation is 80 mg/L, the required sample size for calculation is 23 cases.

In order to ensure that the final analysis of this study has enough sample size, considering the possible loss to follow-up, withdrawal, invalid data and other situations, the maximum sample size of 112 cases estimated based on the above two indicators will be increased by 20%

The dropout rate was expanded to a total sample of 140 cases.

7.2 analysis set

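### The low screening reading that qualifies a patient is also the baseline, with no control group, so a significant rise cannot be called effective at a 2.5% error rate

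*Combined protocol and SAP*

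**What the plan says.** - **Entry (3.3.1).** A patient needs at least two of three signs of malnutrition. The first is "Serum albumin level <3.5g/dL (35g/L", the second "Prealbumin <300mg/L", the third SGA above 7. Everyone enrolled is therefore low on at least one primary marker.
- **Baseline (4.1, Table 1).** One column, "Screening period/baseline", serves both purposes. Both markers are ticked there and next at months 3 and 6.
- **Control (3.1).** "This study does not set up a placebo or control group". Section 1 relies on self-control to reduce interfering factors.
- **Test (7.6.2, 7.7).** A paired t-test of month 6 against baseline for each marker, with Hochberg at one-sided 0.025 and 0.0125.
- **Success rule.** Section 3.2.1: "The treatment was considered effective if the difference in change from baseline for any of the above indicators was statistically significant". Section 7.1 repeats it for month 6 ("prealbumin is statistically significant, it is considered" effective), and 7.7 applies it to the trial as a whole.
- **Run-in.** Section 7.3 mentions 3 months on conventional fluid first, but 4.1 describes only a screening and a treatment phase, and Table 1 has no second pre-treatment measurement.

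**The concern.** A single reading is the patient's usual level plus a temporary deviation. Selecting on low readings selects, on average, downward deviations, and these are gone by month 6. The expected change is then above zero without any treatment effect. Hochberg handles having two endpoints; it does not correct a shifted no-effect change.

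The paired t-test is valid for the hypothesis of no mean change. What fails is the step from a significant change to effectiveness. Section 1 justifies the trial by an uncertain albumin effect and a need for robust evidence, yet the rule cannot separate treatment from regression to the mean, drift or co-intervention. Co-interventions are only partly barred: 5.2 rules out added nutritional support drugs and 5.3 discourages interfering treatments, but 4.1 provides dietary guidance and 5.1.2 allows nutritional support and education.

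**Working it through.** **1. The plan's sample size (7.1).** With one-sided 0.0125 and power 0.90, n = [(2.241 + 1.282) × SD/δ]².
- Albumin: 12.41 × (4.5/1.5)² = 111.7, so 112.
- Prealbumin: 12.41 × (80/60)² = 22.06, so 23.
- With 20% dropout: 112/0.8 = 140.

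All three figures reproduce. (The printed formula lacks the square on the sum of z-values; the stated sizes need it.)

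**2. Smallest significant rise at n = 112.** t(0.975, 111) × SD/√112 = 1.98 × 4.5/10.58 = 0.84 g/L, and 1.98 × 80/10.58 = 15.0 mg/L.

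**3. What a small shift does.** With these SDs of change and a test at one-sided 0.025, a no-effect shift of 0.5 g/L gives a 21.6% rejection rate for albumin, and a shift of 10 mg/L gives 26.2% for prealbumin.

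**4. Model.** Screening reading = usual level + e₁; month-6 reading = usual level + e₂; no treatment effect, no drift. The expected change among those enrolled is −E(e₁ | enrolled), which is positive when low readings are selected.

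From the plan: the two-of-three rule, both cut-offs, the Hochberg rule, SDs 4.5 and 80 (read as SDs of change), and the enrolled means ("it is assumed that the baseline serum albumin before treatment is 27 g/L"; "it is assumed that the baseline prealbumin before treatment is 240 mg/L").

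Assumed, because the documents do not give them:
- total SDs of 5 g/L and 90 mg/L, which imply visit-to-visit correlations of 1 − 4.5²/(2×5²) = 0.595 and 1 − 80²/(2×90²) = 0.605;
- between-patient correlation of the markers 0.4;
- correlation of their same-visit deviations 0 or 0.4;
- SGA above 7 in 50-80% of clinic patients (95% as an extreme), independent of the markers or correlated 0.3 with their usual levels.

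**5. Simulated chance of declaring effectiveness with zero effect, n = 112** (SGA independent / SGA correlated 0.3):

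| SGA above 7 | Deviation correlation 0 | Deviation correlation 0.4 |
|---|---|---|
| 50% | 15.7% / 18.9% | 22.4% / 25.5% |
| 80% | 5.9% / 6.2% | 8.7% / 9.7% |
| 95% | 4.1% / 4.2% | 5.3% / 6.0% |

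At 50-80% the spurious rises are 0.13-0.40 g/L (0.13/1.5 = 9% to 0.40/1.5 = 27% of the planned effect) and 3-10 mg/L (3/60 = 5% to 10/60 = 17%). At 50%, prealbumin is significant in 13-21% of trials and albumin in 4-13%; at 80%, in 4-6% and 3-6%. If all 140 are analysed, the overall range for 50-80% is 7-31%.

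**6. Sensitivity.**
- Total SDs 4-8 g/L and 70-130 mg/L, marker correlation 0.2 or 0.6, SGA above 7 in 30-95%: 3-56%.
- The base case makes 75-91% of clinic patients eligible, above the 20-70% malnutrition quoted in section 1. Wider settings with 43-70% eligible give 15-56%.
- A cruder model (test-retest correlation 0.5-0.9, correlation between the three criteria 0 or 0.4, SGA above 7 in 30-70%) gives 3.9-81%, so 56% is not an upper bound.
- Assumed natural fall of 0.3 g/L and 7 mg/L: base case 0.7-5.6%.
- Assumed rise of 0.2 g/L and 4 mg/L: base case 17-47%.
- Same-visit deviation correlation −0.4: albumin rise about zero, prealbumin still 3-7 mg/L.

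**The case against.** The strongest reply is that the inflation is not established. The total SDs, correlations, SGA prevalence and drift are all assumed, and a modest natural decline brings many settings below 2.5%. On the plan's scale an SGA score of 7 is normal and 8 already abnormal, so scores above 7 may be common in these clinics; at 80-95% the rate is only 4-10%. The malnutrition range in section 1 is not tied to this trial's entry rule, so the 15-56% subset should carry little weight. Section 3.3.2 excludes recent peritonitis or hospitalisation, systemic infection and corticosteroids, which removes some patients with temporarily depressed markers. The spurious rises are below the significance thresholds and far below the planned effects. The uncontrolled design is an open choice for a marketed product.

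Much of this stands as a limit on the size. It does not rescue the rule. The exclusions reduce the bias without removing it. The rule requires significance only, with no minimum effect, and nothing in the design shows whether a decline offsets the bias. The technical-route figure is not shown, so it could not be checked for a second pre-treatment sample, but the text and Table 1 schedule none.

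**Conclusion.** The concern holds. One-sided 0.025 is the error rate for a test of no mean change; it is not the error rate for the conclusion of effectiveness that 3.2.1, 7.1 and 7.7 attach to it. Only the upward direction of regression to the mean is secure, in both markers provided their same-visit deviations are not negatively correlated. Under the base assumptions without drift, the false rate is 16-26% if half of clinic patients have SGA above 7 and 6-10% if 80% do. The documents give no six-month figure for natural decline or for the effect of co-interventions, so the net no-effect change is unknown. Regression to the mean is too small to produce the planned effects; the risk is that a small significant rise is declared proof that the fluid works.

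**What to change.** 1. In 3.2.1, 7.1 and 7.7, state that a significant result shows a rise from baseline, not that the treatment or trial is effective, and read the main objective in 2.1 the same way. This costs nothing and corrects the conclusion on its own.
2. In 3.2.1, Table 1 and 7.6.2, use the screening albumin and prealbumin for eligibility only. For every patient, define baseline as one separate sample taken before the first amino acid bag, by the same assay, as late after screening as the existing 1-month window allows. Keep everyone who qualified at screening, whatever the new value. The cost is one blood tube per patient and one column in Table 1, possibly an extra visit, and no extra patients.
3. In 7.6.2, state that this reduces regression to the mean and removes it only if deviations at the two samples are independent. With no drift and SGA above 7 in 50-80%, the false rate is about 2-3% if they are independent, 4-9% at correlation 0.5 and 4-15% at 0.7. With the assumed upward drift it is still 7-9% under independence, so the rewording is needed in any case.
4. Reconcile the 3 months on conventional fluid in 7.3 with the two phases in 4.1 and with Table 1.

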3.2.2 Secondary endpoints

The secondary endpoint of this study was other relevant indicators of the subjects at 3 months and 6 months after treatment

The body is as follows: Mass (kg): The change in mass of the subject compared to baseline at 3 months and 6 months (Δ Body mass); BMI (kg/m^2): (Δ of the change in BMI of the subject compared to baseline at 3 months and 6 months BMI); CI: CI change value of the subject at 3 months and 6 months compared with baseline (Δ CI);

- Waist circumference and grip strength (cm/kg): The changes in waist circumference and grip strength compared with baseline at 3 months and 6 months were measured by a tape measure to measure the circumference of the narrowest part of the subject. The maximum grip strength of the subjects was measured with a grip strength gauge;
- Arm muscle circumference (cm): The change in arm muscle circumference (Δ arm muscle circumference) of the subjects compared with baseline at 3 months and 6 months was measured by a tape measure at the midpoint of the subject's upper arm and according to the formula

The calculated upper arm muscle circumference = arm circumference (cm) $0.3142 \times$ triceps skinfold thickness (mm);

Δ nPCR (g/kg/d): nPCR change values of subjects at 3 months and 6 months compared to baseline (Δ nPCR);

$\Delta nPNA$ (g/kg/d): Changes in nPNA compared to baseline at 3 months and 6 months
Value ($\Delta nPNA$).

3) Metabolic status-Glycated hemoglobin (%): Glycated hemoglobin of the subjects at 3 months and 6 months compared to baseline. White change value (Δ glycosylated hemoglobin) was measured by an automatic biochemical analyzer to measure the glycosylated hemoglobin of the subjects. Hemoglobin levels.

4) Fasting blood glucose (mmol/L): Fasting blood glucose of the subjects at 3 months and 6 months compared with baseline

Change value (Δ fasting blood glucose) was measured by an automatic biochemical analyzer to measure the subject's fasting blood glucose level.

5) Indicators of residual renal function and dialysis adequacy

- Urine volume: the change in urine volume compared with baseline at 3 months and 6 months (Δ urine volume);

- Ultrafiltration: change in urine volume compared to baseline at 3 months and 6 months (Δ ultrafiltrationmeasure);

Kt/V: The change value of Kt/V compared with the baseline at 3 months and 6 months ($\Delta Kt/V$), calculated by the formula $Kt/V = (V \times \ln(C0/C1) + (V \times UF)/C1)/V$, where V is the body volume, C0 is the urea nitrogen concentration before infusion, C1 is the urea nitrogen concentration after outflow, and UF is the ultrafiltration measure;

Ccr (L/week): the change value of Ccr compared with baseline at 3 months and 6 months (ΔCcr), calculated by the formula $Ccr = (U \times V)/P$, where U is the concentration of urinary creatinine and V is the urine volume, P is serum creatinine concentration;

- PET: PET change values (ΔPET) at 3 months and 6 months compared to baseline

The formula $PET = (D/P) \times 100\%$ was used to calculate the concentration of substances in the effluent D and P. The concentration of a substance in a filling liquid.

6) Capacity load index

Nt-pro BNP: Nt-pro BNP change values at 3 months and 6 months compared to baseline (Δ Nt-pro BNP); the level of Nt-pro BNP in subjects was measured by electrochemiluminescence.

7) Safety endpoint (adverse event): assessed according to vital signs, physical examination, laboratory tests, etc.

3.2.3 Exploratory end point indicators

This study did not set up a separate exploratory endpoint indicator, for exploratory purposes of the indicator (nutritional status and safety comprehensive indicators) are the same as the primary and secondary endpoints.

3.3 Criteria for patient selection and exclusion

This study will be conducted in a multicenter design with five centers expected to enroll 140 subjects.

The inclusion, exclusion and withdrawal criteria of patients in this study are as follows:

3.3.1 Selection criteria

1. Select patients with uremia with malnutrition during the screening period and maintain peritoneal dialysis for at least 3 months. Malnutrition

The standard shall at least meet two of the following items:

(1) Serum albumin level <3.5g/dL (35g/L),

(2) Prealbumin <300mg/L,

(3) Subjective comprehensive nutritional assessment (SGA)> 7 points;

2. Blood urea nitrogen \leq 38mmol/L;

3. The patient is between 18 and 75 years of age;

4. The patient signs an informed consent form.

3.3.2 Exclusion criteria

1. Allergy to any amino acid or excipient in this product;

2. Have had peritonitis more than once in the last 3 months; have had peritonitis or been hospitalized in the last 1 month;

3. Combine hyperthyroidism, systemic infection fever and other diseases of high catabolic state, as well as taking drugs that affect tissues

Metabolic drugs, such as corticosteroids;

4. Congenital amino acid metabolic defects, acute severe pancreatitis, severe hyperbilirubinemia;

5. Malignant tumor metastasis or diffusion, residual cancer after treatment, coagulation dysfunction, aplastic anemia, etc

Patients with serious diseases of other systems such as heart, brain and lung;

6. Kidney transplant may be accepted during the trial;
7. Active hepatitis B or C, cirrhosis, active liver disease, liver dysfunction or human immunodeficiency

The serum test for the defective virus (HIV) was positive.

8. Participants who have participated in other drug clinical trials within 3 months before enrollment;
9. Pregnant and lactating women;
10. A person who is not fit to cooperate;
11. No written informed consent was signed;
12. Inability or unwillingness to comply with the protocol approved by the investigator.

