Treatment Phase: The treatment phase begins after enrollment. Each participant receives a regimen of 1 bag of amino acid peritoneal dialysis and 2-4 bags of glucose peritoneal dialysis fluid daily for 6 months (the amount of glucose peritoneal dialysis fluid is determined based on the treatment plan at the time of screening when the patient enters the study). The amino acid peritoneal dialysis fluid is provided by the research center, with the following composition: amino acids (15). The glucose peritoneal dialysis fluid is also provided by the research center, with the following composition: this product is a compound preparation, each 1L the composition of the solution is 1000mL, alanine 0.951g, arginine 1.071g, glycine 0.510g, histidine 0.714g, leucine 0.850g, lysine 1.020g, 1-lysine hydrochloride 0.955g, methionine 0.850g, phenylalanine 0.570g, proline 0.595g, serine 0.510g, threonine 0.646g, tryptophan 0.270g, tyrosine 0.300g, ammonia 1.393g, sodium chloride 5.380g, Calcium chloride ($\text{CaCl}_2 \cdot 2\text{H}_2\text{O}$) 0.184g, Magnesium chloride (Mg, CL2·6H2O]0.051g), Sodium lactate 4.480g, Ion concentration (mmol/L): Amino acids 87.16mmol/L, Sodium 132mmol/L, Calcium 1.25mmol/L, Magnesium 0.25mmol/L, Chlorine 105mmol/L, Lactate root 40mmol/L. The excipients of this product include hydrochloric acid and water for injection. This product is a glucose-free peritoneal dialysis solution, used as part of the peritoneal dialysis regimen

One part is used for the treatment of chronic kidney patients, especially suitable for peritoneal dialysis patients with serum albumin less than 35g/L.

The composition of glucose peritoneal dialysis fluid is shown in Figure 2:

Drug name	composition					ion concentration					osmotic pressure	pH	capacity
	C6H12O6·H2O	NaCl	C3H5NaO3	CaCl2·2H2O	MgCl·6H2O	Na	Ca	Mg	chloride	lactate			
Low Calcium Peritoneal Dialysis Solution(lactate-G1.5%)	1.5g	0.538 g	0.448g	0.0183g	0.0051g	132.01	1.25	0.25	95.04	39.97	344	4.5-6.5	2000
Low Calcium Peritoneal Dialysis Solution(lactate-G1.5%)	2.5g	0.538 g	0.448g	0.0183g	0.0051g	132.01	1.25	0.25	95.04	39.97	395	4.5-6.5	2000
Low Calcium Peritoneal Dialysis Solution(lactate-G4.25%)	4.25	0.538 g	0.448g	0.0183g	0.0051g	132.01	1.25	0.25	95.04	39.97	483	4.5-6.5	2000

Figure 2. Composition of glucose peritoneal dialysis fluid

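### Section 7.3 presumes three months on conventional fluid before treatment, but no entry criterion, study phase or visit secures it, so a current or recent user of the marketed amino acid fluid could enter with an on-treatment baseline

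*Combined protocol and SAP*

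**What the plan says.** Section 3.1 sets the comparison: "each participant serves as their own control before and after receiving amino acid peritoneal dialysis fluid treatment". The same section gives as one reason for having no control group that "amino acid peritoneal dialysis fluid is already on the market".

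Selection item 1 in section 3.3.1 reads "Select patients with uremia with malnutrition during the screening period and maintain peritoneal dialysis for at least 3 months". It does not say which fluid. Of the twelve exclusions in section 3.3.2, the closest to a prior-exposure rule is item 8: "Participants who have participated in other drug clinical trials within 3 months before enrollment". Exclusion 3 covers drugs that affect tissue metabolism and gives corticosteroids as its example; it does not name dialysis fluid. The synopsis repeats these lists.

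Section 7.3, explaining why there is no randomisation, says that each subject was first on conventional peritoneal dialysis fluid for 3 months. Section 4.1 has only two phases: screening, within the month before enrolment, and treatment. Table 1 has one screening/baseline column and then months 1 to 6.

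For the sizing in section 7.1, "it is assumed that the baseline serum albumin before treatment is 27 g/L", and the albumin inputs are "δ is 1.5g/L, and the standard deviation is 4.5 g/L".

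**The concern.** In a before/after design without a parallel arm, the treatment effect is whatever separates the follow-up value from the baseline value. That needs a baseline free of the study fluid. Section 7.3 shows that the authors had this in mind, but sites enrol from section 3.3, and nothing there asks about it.

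For a patient already on the fluid at screening, the comparison is fluid against the same fluid, and little change is to be expected. For one who stopped recently, the baseline may still be partly treated. Either case pulls the albumin and prealbumin changes towards zero, along with the secondary measures and the before/after safety measures (Nt-pro BNP, Kt/V, Ccr, ultrafiltration and urine volume).

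Adverse events work differently. Section 4.1 item (17) counts them from the start of treatment, so a treated baseline does not dilute them. Their rates could still be understated for new users if prior users are a group already selected for tolerating the fluid.

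**Working it through.** **Does the text secure the baseline?**

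| Place | What it requires about prior fluid |
|---|---|
| 3.3.1 item 1 | 3 months of peritoneal dialysis, fluid not specified |
| 3.3.2 items 1 to 12 | nothing; item 8 concerns other drug trials only |
| 4.1, study phases | no lead-in phase |
| Table 1 | no lead-in visit; past illness and treatment recorded at screening |
| 7.3 | 3 months on conventional fluid, stated as fact for every subject |

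Only section 7.3 carries the condition, and it is not an enrolment rule.

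**Reproducing the plan's sample size.** The inputs from section 7.1 are one-sided 0.0125, power 0.90, albumin δ = 1.5 and SD = 4.5 g/L, prealbumin δ = 60 and SD = 80 mg/L.

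- n = (z₀.₉₈₇₅ + z₀.₉₀)² × SD²/δ², with (2.2414 + 1.2816)² = 12.411
- Albumin: 12.411 × (4.5/1.5)² = 111.7, so 112
- Prealbumin: 12.411 × (80/60)² = 22.06, so 23
- Enrolment: 112/0.80 = 140

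All three figures agree with the plan.

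**Effect of prior users.** Let f be the share of prior users. The documents do not give it, so the values below are assumptions. As a worst case, suppose that prior users gain 0 and the others gain the planned 1.5 g/L.

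- Mean change = 1.5 × (1 − f)
- SD = √(4.5² + f(1 − f) × 1.5²)
- Power is from the noncentral t, one-sample test, n = 112

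| f | Mean albumin change (g/L) | SD (g/L) | Power at one-sided 0.025 | Power at one-sided 0.0125 |
|---|---|---|---|---|
| 0 | 1.50 | 4.500 | 0.938 | 0.894 |
| 2% | 1.47 | 4.505 | 0.928 | 0.880 |
| 5% | 1.425 | 4.512 | 0.912 | 0.856 |
| 10% | 1.35 | 4.522 | 0.879 | 0.811 |
| 20% | 1.20 | 4.540 | 0.792 | 0.700 |
| 30% | 1.05 | 4.552 | 0.677 | 0.568 |

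Under the Hochberg rule in section 7.7, albumin is in effect tested at 0.025 whenever prealbumin also passes 0.025. It is tested at 0.0125 otherwise. On the plan's assumptions prealbumin almost always passes, so the 0.025 column is the operative one.

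**Prealbumin.** With mean 60 × (1 − f) and SD inflated in the same way, power at n = 112 and one-sided 0.0125 is at least 0.998 for every f up to 30%. At f = 30% the mean is 42 mg/L, the SD 84.6 mg/L and the power 0.998.

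**The case against.** The strongest reply is that the plan does state the condition. Section 7.3 applies it to every subject, it matches the 3 months of dialysis in selection item 1, and section 3.1 defines the control as the state before the fluid. A reader might infer from section 3.3 alone that the plan never intended an untreated baseline. The documents do not support that: the intention is there. What stands is that it is not carried into the criteria, the phases or the visit table, which are what a site applies.

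A second reply is that prior use is conjecture. No document gives a rate of use at the five centres. Section 4.1 calls the product "especially suitable for peritoneal dialysis patients with serum albumin less than 35g/L", which would make earlier use in this population likely, but section 5.1.1 says the opposite about the same patients. Those two statements must be reconciled, and until then neither shows how common prior use is. This stands: enrolment of prior users is permitted, not shown. That the fluid is marketed is enough to make it possible.

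A third reply is that the numbers are a worst case and that the trial's conclusion hardly moves. Zero gain overstates the loss for patients who have stopped the fluid. If prior users are few, the cost is small: at 2%, albumin power goes from 94% to 93%. Success needs only one of the two endpoints, and prealbumin has ample margin. The bias is also towards no effect, so it does not produce a false claim of benefit. All of this stands, and it limits the point to the albumin result and the effect sizes.

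Finally, section 4.1 item (4) already records current medications and other treatments, so prior users might be traceable. That is true, but recording neither excludes them nor specifies an analysis without them.

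**Conclusion.** The point holds as a gap between section 7.3 and the enrolment rules. As section 3.3 is written, a current or recent user of the amino acid fluid is eligible, and that patient's baseline would not be the untreated value that sections 3.1 and 7.1 rely on.

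Its size depends on f, which is unknown, and on the worst-case assumption of no gain in prior users. The mean albumin change shrinks in proportion to f. At f = 10%, albumin power falls by about 6 points at one-sided 0.025 and about 8 points at 0.0125. At f = 20%, it falls to 79% and 70%.

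Two stronger readings are not supported. A reader might infer that the trial's overall success is in jeopardy; prealbumin power of at least 0.998 up to f = 30% says otherwise on the plan's own figures. A reader might also infer that harms will be under-reported; for adverse events that is only a possibility, through selection for tolerance. The correction is worth making because it is cheap and decides who enters the comparison.

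**What to change.** Reconcile section 7.3 with sections 3.3 and 4.1 and the synopsis. Add an eligibility criterion such as: no use of any amino acid peritoneal dialysis fluid in the 3 months before the baseline blood sample. Three months is the period that section 7.3 itself gives.

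Record prior dialysis fluid, with the date of last use, under the existing previous illness/treatment item in Table 1. If patients are already enrolled, flag prior users and repeat the primary analysis and the adverse-event summary without them.

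The cost is a protocol amendment with one criterion and one CRF item, and no added visits or tests. Recruitment may be slightly slower because current and recent users cannot enter.
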